## 1. INTRODUCTION

### 1.1. BACKGROUND

Surgical resection of brain tumours is challenging from both an anatomical and functional perspective. The goal of the neurosurgeons is to remove as much tumour tissue as possible, while preserving surrounding normal brain. This often remains a utopic goal. Brain tissue around the tumour is in fact quite rarely completely normal, as it is invaded by tumour cells, and the tumour margins are not clearly defined, but fade into normal tissue. In order to overcome this problem, current trend in neurosurgery is to push the margins of resection beyond the obvious tumour boundaries and try to resect also those areas of the brain that the surgeon suspects have been invaded by tumour cells. However, this choice also poses some problematic challenges. The main obstacle to a generous resection is the presence of the so-called “eloquent areas” of the brain, that is, regions of the brain not amenable to be resected otherwise the patient will unequivocally develop a permanent disability (e.g. paralysis / mutism / visual impairment / etc.). Therefore, the concept of “functional margins” of resection has been popularized in neurosurgery: tumour resection is carried out up to the point where an eloquent area of the brain is reached. The resection is stopped at that point in order to spare that specific functional area.

Identifying and preserving eloquent brain areas is possible thanks to technological advancements in the field of neurophysiology. Neurophysiological monitoring techniques include a series of continuous tests performed during surgery, either with the patient fully sedated, or conscious during surgery (in this case the procedure is performed under local anaesthesia). Although feasible, this solution is not overly practical nor completely reliable. Experienced and extensively trained anaesthetic, surgical and neurophysiological teams are an indispensable requirement. Even so, false positives or false negatives can occur, reducing the extent of surgical resection in the first case, or increasing the likelihood of a post-operative impairment in the second.

## 1.2. RATIONALE FOR THE CURRENT STUDY

With the present research project, we are aiming to test a technology that could potentially improve the extent of resection of brain tumours. The main goal is to develop an instrument capable of better identifying differences between brain tumours margins and normal brain tissue, and differences between functionally active areas of the brain (“eloquent areas”) and non-eloquent areas, thus allowing the surgeon sparing them while performing an aggressive surgical resection on the tumour tissue.

From a theoretical standpoint, one way to distinguish tumour tissue from the surrounding brain is to study the micro-architecture of blood vessels, the pattern of blood perfusion, and the levels of oxygenation / deoxygenation. A subset of radiological and molecular studies has focused on this point [1-2]. Moreover, functional Magnetic Resonance Imaging (fMRI) is based on a similar concept [3], as it analyses the differences in oxyhaemoglobin and deoxyhaemoglobin in specific brain areas during the execution of a task. The intra-operative analysis of differences in blood perfusion and micro-architecture is a relatively poorly explored field so far. Most of the studies are pre-clinical and have been performed on animals or animal models [4-7], and are mostly focused on different body districts.

The hardware behind multi-spectral analysis consists in a dedicated camera analysing the reflected light from a tissue, and dividing it into smaller wavelengths. Specific tissue tends to reflect different wavelengths; therefore, the spectral analysis can potentially detect subtle differences in tissue composition. Multispectral analysis has already been used in lung, colon, skin, and head and neck surgery in pre-clinical and clinical studies [7-13]. Preliminary results show different blood volumes and oxygenation rates in different tissues, meaning that the technology can be used to study discrepancies in appearance of tumour tissue as opposite to normal mucosa [7][9] [11-12]. The main advantages of this technology are that: it is non-invasive, costs are low, the machinery is not particularly bulky thus the hindrance in theatre is limited, and the acquisition time is short.

## 2. STUDY OBJECTIVES

The present study aims to investigate the potential application of multispectral analysis, hyperspectral imaging, and fluorescence during neurosurgical procedures, specifically during brain tumour resection. The research procedure consists of images acquisition and data processing, with virtually no additional invasive procedures to be performed on patients.

*Study aims:*

- 1) detect structural differences between brain tumour tissue and surrounding brain;
- 2) detect structural differences between eloquent/functional and non-eloquent/non-functional brain areas;
- 3) test whether the combination of multispectral/hyperspectral analysis and fluorescence could provide additional information about the structural differences of brain tumours VS normal brain tissue.

## 3. STUDY DESIGN

*Type of study:* pilot study - prospective cohort study

*Estimated total study duration:* 3 years

*Planned study sites:* Imperial College of London and Imperial College NHS Trust

*Sample size:* 50 patients

### 3.1. STUDY OUTCOME MEASURES

*Primary outcome measures:*

The primary outcome measure will be the analysis of spectroscopic signal reading of:

- brain tissue and tumour tissue;
- functional brain areas and non-functional brain areas.

In order to analyse differences between brain tissue and tumour tissue, the signals collected will be correlated both to the visual signal seen on normal operative field and the signal seen on the peri-operative imaging (MRI scan).

In order to analyse differences between eloquent and non-eloquent brain areas, the signal collected will be correlated with the neuro-physiological intra-operative findings, in every case there is an indication to do so, and with the expected location of the eloquent areas on the peri-operative images.

#### Secondary outcome measures:

The secondary outcome measure will be the analysis of spectroscopic signal reading of surgical field as seen at its baseline and under fluorescence-specific light.

## 4. PARTICIPANT ENTRY

The present project consists of a pilot observational study on patients diagnosed with brain tumours candidate for a neurosurgical operation.

Patients will be recruited following the inclusion criteria: any patient with a diagnosis of brain tumour, age ranging from 18 with no upper limit, who will agree to the operation and to take part of the present study, will be enrolled.

The present study will include:

- In vivo microscopic and/or endoscopic multispectral/hyperspectral analysis;
- In vivo microscopic and/or endoscopic fluorescence (using either infrared light - IR - or ultraviolet light, depending on the clinical indication of the specific case);

- In vivo microscopic and/or endoscopic fluorescence combined with multispectral/hyperspectral analysis.

Enrolment will proceed for 3 years, with the possibility of stopping the research at an earlier date if a sufficient amount of data is collected for a reliable statistical analysis. From a practical point of view, participation in the study will only imply that some images will be acquired during surgery and processed at a later stage. The study won't impact on patients' care at any stage, nor will produce results that will be relevant for future medical records of patients enrolled. Patients will be approached about this study at the time of their first neuro-oncology clinic consultation – this might not necessarily be the clinic where the diagnosis will be given for the first time, as these patients are often referred from other centres where the diagnosis has already been communicated. A member of the research team who is also involved in direct care will be present at the time of the consultation and will explain in details what are the purposes and the methods of the present study. The patient will be given a PIS at this point.

Consent will be taken by a member of the research team. Consent will be sought at preoperative assessment or in a private room in the admissions lounge, in the clinic, or in the hospital ward, in CXH. Consultation length can vary depending on the complexity of the clinical procedure planned. Surgery is usually scheduled at least a few days after the clinic consultation, in most cases a few weeks after, in a minority of cases some months after. If the patient agrees to take part in the study, the patient will sign the consent form for research within the day before the surgery, thus allowing sufficient time for questions and autonomous research about the topic.

#### 4.1. MATERIALS AND METHODS

A Liquid Crystal Tunable Filter (LCTF) camera will be used for the purpose of the present study. The camera has been assembled by Imperial College of London and will be connected to the operative microscope and endoscope. The whole system (microscope + attached camera) will be draped using sterile drapes as per standard procedure in neurosurgery. The camera itself is in turn connected also to a dedicated computer with dedicated software for

images acquisition. The instrument has been previously used in other studies performed by some of the research team members [12-13].

Patients who have agreed to take part in the present study will be admitted in Charing Cross Hospital, Neurosurgery Department, 11th floor, south corridor. The day before the surgery, as standard NHS practice for these procedures. Except for further discussion on the details of the study and signing the consent form for research, there won't be any additional test required for the patient other than those for standard NHS clinical care. The day of the surgery, the procedure will be carried out as expected per clinical indication. Surgery will be performed in Charing Cross Hospital, 14th floor, Theatre area. The caring surgeons will also be members of the research team.

The patient will be anesthetized and be placed on the surgical table. WHO checklist will be performed and the operating procedure will be carried out as standard NHS practice. During surgery, the operating surgeon will be using standard NHS neurosurgical equipment such as an endoscope and/or a microscope. From the surgeon's perspective, this equipment is operated in exactly the same way as with any other procedure. The only technical modification would be that either the microscope or the endoscope in use will be connected to the system of camera and filters for multispectral/hyperspectral analysis. Use of this imaging acquisition technique will not change standard operative practice, nor will it interfere with the principles of neurological surgery. During each surgical intervention, tissue-specific spectral data will be collected at specific stages - mostly once the brain surface is exposed and at the end of the resection on the surgical cavity. It is important that there is a method of comparing the spectral data generated by multispectral imaging to the nature of the tissue being dissected. In order to do this, we plan to visually record the operation in order to sync visual data with the spectral data obtained at the same moment in time. The video recording will not be patient identifiable and will be viewed only by members of the research team working on this project (see below). The use of video recording equipment will be included in the patient information sheet given to all patients prior to gaining consent.

Pseudo-anonymized clinical data will also be collected on College computers to be matched with intra-operative data. Specifically, the researchers will collect:

- clinical data such as diagnosis, age, sex, clinical status, medical background – this data collection will be performed to ensure that our population is homogeneous according to common statistical parametric tests; moreover, some clinical information (such as the neurological baseline of the patient) will be crucial in order to quantify exactly the degree of reliability of the multispectral signal for eloquent areas detection;
- radiological and histological data – this data collection will be performed for the purpose of the correlation between the multispectral signal and the radiological and/or histological findings;

Surgery will be conducted following standard procedures, already validated in clinical practice. The surgeons performing the procedures will be [name] [name] (CI), [name] (PhD student and clinical fellow), [name] (Consultant Neurosurgeon), and [name] (Neurosurgery Trainee and Clinical Lecturer). Surgeons will work in teams, each team with no more than two surgeons. [name] and one of his collaborators will be present in theatre to facilitate images acquisition. For each researcher not normally involved in clinical practice, research passport will be provided. Intra-operative imaging data and spectra will be collected during tumour resection, but the analysis on the spectra will be performed on a different time and setting, in order not to excessively prolong the surgical procedure.

Researchers will collect spectral data up until the statistical model used for multivariate analysis does not longer improve the degree of accuracy (see Section 6 - statistical analysis).

## 4.2. CONFIDENTIALITY

Each patient will be given a specific protocol number – ID log. Anonymous video recording and/or images acquisition will be carried out by the team members in order to sync spectral data collected with the surgical procedure and will be linked with the ID log. These data will be hosted in secured Imperial College Computers, and College Server, accessible only by members of the research team, and under password protection.

Regarding clinical data, these will be stored on NHS Trust Encrypted computers in a semi-anonymized form and transferred on College Computers in a pseudo-anonymized form if needed for study purposes. NHS computers follow NHS Trust confidentiality policy and comply with the Data Protection Act. Semi-anonymization means that these data will include NHS number, Hospital Number, age, protocol number. If for study purposes, the team will need to transfer these data to College Computers, pseudo-anonymization will be performed prior to transfer clinical data to the College computers. Pseudo-anonymization means that these data will NOT include any identifiable information, including NHS number and hospital number, but only the protocol number – ID log.

PID (Personal Identifiable Data) will be stored for 10 years as per College retention policy.

Signed consent forms will be archived inside the patients' medical records and will be available for any audit and research quality control activities. Patients will be given a copy of the signed consent form. A Trial Master File (TMF) containing hard copies of the consent forms will be kept in the Neurosurgery Department in Charing Cross Hospital 3S (offices). Entry into these facilities is restricted and controlled in hours. A specific code is required to access the facility out of hours, and only members of staff have access. No other copies will be done or retained.

#### **4.3. INCLUSION CRITERIA:**

- Above the age of 18, no upper age limit
- Sex: male or female
- Candidates for surgery due to a confirmed clinical and radiological diagnosis of cranial intrinsic or extrinsic tumour – any histological diagnosis confirming neuro-oncological disease, including primary and secondary disease
- Agreed to take part to the present research protocol and signed proper informed consent form

#### 4.4. EXCLUSION CRITERIA:

- Suspected differential diagnosis of pathological condition affecting central nervous system other than neuro-oncological disease - including demyelinating diseases, infections, brain traumas / haematomas, vascular or auto-immune diseases
- Patients not capable to give consent – not in condition of understanding, processing and retaining information

### 5. ADVERSE EVENTS

As per the definition of adverse event (“Adverse Events (AEs) are any unfavourable and unintended signs, including abnormal laboratory results, symptoms or a disease associated with treatment.” - <https://www.nbt.nhs.uk/research-innovation/running-your-study/safety-reporting/classification-adverse-events>), we do not expect for this technology to cause any adverse event whatsoever. The light sources are the same used in every standard neurosurgical procedure. The only real difference that the acquisition will make is to prolong time of the surgery by approximatively 5 minutes for each acquisition at the most.

The worst-case scenario will be that of technical failure of the acquisition, with no possibility of data storage or analysis. This will not impact in any form on patient’s treatment and outcome. In the very unlikely occurrence of a SAE, standard procedures will be followed, as described below.

#### 5.1. NON SERIOUS AEs

All such events, whether expected or not, will be recorded and notified by the investigators to the CI.

## 5.2. SERIOUS AEs

An SAE form should be completed and faxed to the Chief Investigator within 24 hours. However, relapse and death due to the diagnosis (brain tumour and/or vascular anomaly), and hospitalisations for elective treatment of a pre-existing condition do not need reporting as SAEs.

All SAEs should be reported to the REC where in the opinion of the Chief Investigator, the event was:

- ‘related’, ie resulted from the administration of any of the research procedures; and
- ‘unexpected’, ie an event that is not listed in the protocol as an expected occurrence

Reports of related and unexpected SAEs should be submitted within 15 days of the Chief Investigator becoming aware of the event, using the NRES SAE form for non-IMP studies. The Chief Investigator must also notify the Sponsor of all SAEs.

Local investigators should report any SAEs as required by their Local Research Ethics Committee, Sponsor and/or Research & Development Office.

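### The serious adverse event rule exempts tumour-attributed deaths with no time limit, so a death soon after the imaged operation may need no formal report

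*Combined protocol and SAP*

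**What the plan says.** Section 5.2 opens with the main reporting duty: "An SAE form should be completed and faxed to the Chief Investigator within 24 hours". The next sentence carves out exceptions. Among them is "relapse and death due to the diagnosis (brain tumour and/or vascular anomaly"), and the listed events "do not need reporting as SAEs". The section gives no period to which the exception applies, no criteria for calling a death due to the diagnosis, and no person who decides.

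The other duties in section 5.2 are framed in terms of SAEs. For the sponsor: "The Chief Investigator must also notify the Sponsor of all SAEs". For local bodies: "Local investigators should report any SAEs as required by their Local Research Ethics Committee, Sponsor and/or Research & Development Office". The ethics committee receives those SAEs that the Chief Investigator considers both related to the research procedures and unexpected. Section 5.1 deals with non-serious events only.

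On the expected safety profile, section 5 states: "we do not expect for this technology to cause any adverse event whatsoever". It accepts that each acquisition may lengthen the operation by up to about 5 minutes. Section 4.1 adds: "The caring surgeons will also be members of the research team".

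Section 4.4 excludes patients in whom a non-oncological condition is suspected, including "infections, brain traumas / haematomas, vascular or auto-immune diseases".

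**The concern.** An exemption for death from the underlying disease is reasonable in long follow-up of patients with cancer, where such deaths are expected and say little about the research. It fits less well here. Imaging takes place during the operation, so any harm from it, including harm from added operating time, would most plausibly appear in the following days. In those days the effects of tumour, surgery and research are hardest to separate. The exemption requires that separation to be made first, before anything is reported.

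What is at stake is oversight, not an efficacy result. If an early death can be set aside on attribution alone, the sponsor cannot check the expectation of no adverse events against a complete list of early deaths.

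**Working it through.** The point is about the reporting rule, and the plan has no figure to reproduce. The check follows two early post-operative deaths through each route in sections 5.1 and 5.2.

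| Route | Section | What triggers it | Death classed as due to the tumour | Death attributed to surgery, anaesthesia or imaging |
|---|---|---|---|---|
| SAE form to the Chief Investigator | 5.2 | SAE not exempted | Not required | Required within 24 hours |
| Chief Investigator's relatedness opinion | 5.2 | Event handled as an SAE | Not triggered | Triggered |
| Notice to the sponsor | 5.2 | Any SAE | Not triggered | Triggered |
| Report to the ethics committee | 5.2 | SAE judged related and unexpected | Not triggered | Within 15 days, if so judged |
| Report to local bodies | 5.2 | Any SAE | Not triggered | As locally required |
| Record and notice to the Chief Investigator | 5.1 | Non-serious event | Does not apply | Does not apply |

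The two columns differ only in the cause assigned. No other section in the available text requires deaths around the operation to be reported. One consequence is odd: section 5.1 sends every non-serious event to the Chief Investigator, expected or not, while a tumour-attributed death two days after the operation may generate no form.

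**Availability of the exempting cause.** The inclusion criteria (section 4.3) admit only candidates for surgery for a cranial tumour, primary or secondary. The exempting diagnosis is therefore present in all 50 planned patients.

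**Size of the research exposure.** Section 5 gives up to about 5 minutes per acquisition. Section 6.3 gives an average of 6 datasets per patient. Section 4.1 says that data are collected mostly at two stages. The documents do not say how datasets map to acquisitions, so only a range follows:

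- one acquisition per stage: 2 × 5 = 10 minutes at most;
- one acquisition per dataset: 6 × 5 = 30 minutes at most, on average.

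**Number of deaths.** The documents give no peri-operative mortality. As an assumption, take 1% to 4% from all causes:

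- 0.01 × 50 = 0.5 deaths;
- 0.04 × 50 = 2 deaths.

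These include deaths attributed to surgery or anaesthesia, which are already reportable. The exempt deaths are some unknown part of 0.5 to 2.

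**Vascular anomaly.** Section 5.2 names it as a diagnosis under study, while section 4.4 excludes suspected vascular disease. If the exclusion works, the term should apply to no enrolled patient. It looks like a leftover, and the two sections should be reconciled.

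**The case against.** The strongest reply is that the exemption is narrow. Haemorrhage, infection, anaesthetic complications and anything linked to the imaging are not covered. Serious complications that precede a death go to the Chief Investigator and on to the sponsor without any relatedness test. Nothing in the text invites anyone to relabel an operative death as a tumour death. The operation is clinically indicated standard care, and the study adds only imaging time. Safety is neither a primary nor a secondary outcome, and no end-of-study safety claim is planned.

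All of this stands, and it limits the point. It does not close the gap, because nothing governs how an early death is classified and one classification removes every formal route.

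A reader might go further and infer any of the following. The documents do not support them.

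- *The Chief Investigator is kept in the dark.* Section 4.1 lists the Chief Investigator among the operating surgeons, who may well learn of a death informally. What is missing is the formal report and, with it, the notice to the sponsor.
- *The operating surgeons decide the cause of death.* They belong to the research team, and the exemption acts before a form is sent, so this is plausible. But no section names the person who decides.
- *Nobody outside the operating team sees safety events, or every peri-operative death could go unreported.* The first is wrong, since all other SAEs go to the sponsor. The second is a worst case that needs every death to be attributed to the tumour.

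**Conclusion.** The point holds in a limited form. As written, an early post-operative death classed as due to the tumour triggers no required report and no relatedness review, because the exemption has no time limit and all the serious-event routes depend on SAE status. Deaths given another cause are unaffected.

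The size is small: some part of 0.5 to 2 deaths in 50 patients, under an assumed mortality of 1% to 4%. Severity is minor in an observational imaging study, and the change is worth making because it is cheap. The conclusion rests on the readable text. Part of the document directly after section 5.2 was not available, and nothing is assumed about it. The mismatch over vascular anomaly is editorial.

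**What to change.** In section 5.2:

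1. Require every death from the start of the imaged operation to the end of a fixed peri-operative window to be reported to the Chief Investigator and the sponsor, whatever the presumed cause. Discharge or 30 days, whichever is later, is one example of such a window. Discharge alone would still miss a death shortly after an early discharge.
2. State that relatedness is assessed after the report is made, not as a condition for making it.
3. Apply the exemption for relapse and tumour death only after the window closes.
4. Reconcile the reference to vascular anomaly with the exclusion criteria in section 4.4.

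Asking another surgeon from the same team to judge relatedness is not recommended. It would add little independence, and with teams drawn from four named surgeons it could leave a trainee assessing a senior colleague's case.

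The cost is a few lines of protocol wording and a few extra forms for events already in the hospital record. Only reporting changes. Clinical care does not.
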